5.2 Screen Failures

Screen failure data will be tabulated by reason subjects were found to not be eligible for the study.

5.3 Protocol Deviations

Protocol deviations will be identified prior to the database lock and unblinding, and the Per-Protocol Population will be determined based on a review of those deviations. Protocol deviations will be tabulated and listed, indicating major/minor. In addition, a listing of subjects for whom the treatment blind was broken during the study will also be provided, if appropriate.

5.4 Demographic and Baseline Characteristics

Demographics and baseline characteristics will be summarized for the Safety Population.

- The variables to be included in the summary are age, sex, race, ethnicity, baseline body weight, height, body mass index (BMI), history of smoking, baseline MMSE, dementia type, fall history, and caregiver-adapted Falls Efficacy Scale – International.
- Details of the primary caregiver (relationship to subject, live with the subject) will be included in a tabulation.
- All demographic data will be tabulated overall and then by sequence.
- Other characteristics collected on the CRF will be listed as appropriate.

5.5 Subject Inclusion and Exclusion Criteria

Subjects not meeting specific eligibility criteria questions will be listed.

5.6 Medical History and Medical Conditions Present at Entry

Past and current medical conditions will be collected and coded using the Medical Dictionary for Regulatory Activities (MedDRA), using Axovant Sciences coding conventions.

A tabulation displaying medical history will be provided by system organ class (SOC) and preferred term for the safety population.

5.7 Prior and Concomitant Medications

Prior and concomitant medication verbatim text will be coded using the World Health Organization's Drug Dictionary (WHO-DD), and will be classified according to the default Anatomical Therapeutic Chemical (ATC) classification system code, WHO-DD Drug Name, and preferred term.

Medications will be tabulated as:

- Prior medications
- Concomitant medications
 - Single-blind run-in and washout periods
 - Double-blind periods

Medications received prior to the date of first dose of single-blind investigational product are considered as prior medications. Medications will be considered as concomitant if the start date of the medication is on or after the date of first intake of investigational product or if the start date is prior to the first date of investigational product, but the medication is ongoing during the treatment period in the study.

Concomitant medications will be further split by concomitant medications taken during the Single-Blind Placebo Run-In Periods and concomitant medications taken during the Double-Blind Treatment Periods. Those will be presented by treatment group. It should be noted that a concomitant medication can be counted in more than one period.

Use of non-investigational products will be summarized (number and percentage of subjects) by treatment, the highest ATC class level, and preferred term for the safety population.

A listing of non-medication therapy will be provided.

5.8 Extent of Treatment Exposure

Duration of exposure for the Double-Blind Treatment Period (Period II and Period IV) will be calculated by treatment group as follows:

- Duration of exposure in days = (Double-Blind Treatment Period stop date – Double-Blind Treatment Period start date) + 1

Duration of exposure will be tabulated descriptively and categorized as:

- 0 to 1 week
- >1 to 2 weeks
- >2 weeks

Note: Duration of exposure will exclude any dates with documented dose interruptions.

5.9 Treatment Compliance

Compliance with study drug will be assessed during the run-in and over the Double-Blind Treatment Periods (Period II and Period IV) using drug dispensing records. Treatment compliance during the double-blind period will be computed by determining the number of tablets taken relative to the number of tablets expected. Subjects are expected to take one tablet per day of each.

Treatment compliance based on the drug accountability per subject/period will be calculated as follows:

- Compliance (%) = (number of tablets taken in the period)/(number of tablets expected)*100

- Number of tablets taken = the number of tablets dispensed in the period – the number of tablets returned
- Number of tablets expected = (date of the last dose - date of the first dose + 1 in the period)

Summary of treatment compliance will be presented by treatment group. The number and percentage for compliance expressed as a categorical variable (<80%, ≥80% to ≤120%, and >120%) will also be presented by treatment group.

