## 7. STUDY TREATMENT

### 7.1. Investigational Product and Other Study Treatment

IP in this study is defined as 35 mg RVT-101 tablets and their matching placebo, and will be provided by Axovant Sciences. RVT-101 and placebo tablets will be indistinguishable from each other. All subjects will take one tablet of IP daily in the morning, with or without food; this will consist of either one tablet of 35 mg RVT-101 or one tablet of placebo.

IP for Period I (the Single-Blind Run-In Period, Weeks -2 to 0) will be supplied at Visit 2. Subjects will be given 1 bottle of placebo tablets at this visit. Each bottle will contain 50 tablets, which is sufficient medication for 2 weeks plus 36 days' overage. Subjects will be instructed to take one tablet of IP daily in the morning with or without food. Subjects will take the first dose of investigational product from this bottle in clinic at Visit 2.

IP for the Periods II, III, and IV (Double-Blind Treatment Periods and Washout Period), Weeks 0 to 6) will be supplied at Visits 3, 4, and 5. At each dispensing visit during the Treatment Period, subjects will be given one bottle of IP. Depending on treatment assignment, subjects will receive either one bottle of 35 mg RVT-101 tablets or one bottle of placebo tablets. Subjects will not know which treatment they are taking. Each bottle will contain 50 tablets, which is sufficient for 2 weeks plus 36 days' overage. Subjects will be instructed to take one tablet of IP daily in the morning with or without food. Subjects will take the first dose of investigational product from each bottle in clinic at Visits 3, 4 and 5.

New bottles of IP will not be dispensed at Visit 6. Drug accountability will be checked at Visits 3, 4, 5 and 6.

All subjects and their caregivers should be instructed to return IP bottles, with any unused drug, to each visit.

Acetylcholinesterase inhibitor background therapies will not be supplied by the sponsor.

Characteristic	Investigational Product	
	Investigational Product	Placebo
Product Name:		
Formulation Description:	pink, film-coated, round tablets	pink, film-coated, round tablets
Dosage Form:	35 mg Tablet	Placebo Tablet
Unit Dose Strength(s)/ Dosage Level(s):	35 mg 35 mg	N/A placebo
Route of Administration:	Oral	Oral
Duration (Run-in Period):	N/A	2 weeks
Duration (Treatment Periods):	2 weeks	2 weeks
Duration (Washout Period):	N/A	2 weeks

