#### **7.6. Compliance with Investigational Product Administration**

When subjects are dosed at the site, they will receive IP directly from the investigator or designee, under medical supervision. The date and time of each dose administered in the clinic will be recorded in the source documents. The dose of IP and study subject identification will be

confirmed at the time of dosing by a member of the study site staff in addition to the person administering the IP.

Every effort should be made to encourage subject compliance with the dosage regimen as per protocol for IP. The investigator is responsible for discussing methods to ensure high treatment compliance with patients and caregivers before randomization. All subjects and their caregivers should be instructed to return IP bottles with any unused drug at each visit to the investigator or designee. A record of the supplies dispensed, taken, and returned will be made in the case report form at each visit. The investigator or designee is responsible for reconciling the number of tablets returned with the expected number of tablets to be taken by a study subject and accounting for any discrepancies.

Subjects should be withdrawn from the study where there has been a failure to take double-blind IP for a period exceeding 3 consecutive days or for more than 5 days in total within one of the 2-week, double-blind treatment periods. In addition, subjects should not have missed any double-blind doses of IP within the 2 days before gait testing is performed; subjects who have missed a dose of IP within the 2 days before gait testing is performed should have their study visit rescheduled to a different day within the visit window. While interruptions in IP administration should be avoided wherever possible, short-term interruptions ( $\leq 3$  days) due to forgetfulness, caregiver illness or absence, a pause in IP administration required during an intervention, hospitalization, or while a subject considers the study continuation, or for any other reason are not necessarily grounds for automatic withdrawal but should be assessed by the investigator and discussed with the medical monitor.

Other major protocol violations as well as use of prohibited drugs (see Section 7.9.2) may be cause for discontinuation of IP or withdrawal from the study.

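### The SAP compliance denominator stops at the last dose taken, so doses missed at the end of a completed period go uncounted in the descriptive compliance table

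*SAP*

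**What the plan says.** SAP 5.9 (Treatment Compliance) computes, per subject and period, "Compliance (%) = (number of tablets taken in the period)/(number of tablets expected)*100". The numerator is "Number of tablets taken = the number of tablets dispensed in the period – the number of tablets returned". The denominator is "Number of tablets expected = (date of the last dose - date of the first dose + 1 in the period"). The percentage is summarised by treatment and also banded as below 80%, 80% to 120%, and above 120%.

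SAP 4.1.5 ends each double-blind period on the last dose date, so the words about the period in the formula do not bring later scheduled days back in.

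On supply, Protocol 7.1 states: "Each bottle will contain 50 tablets, which is sufficient for 2 weeks plus 36 days' overage". One bottle is given at each dispensing visit, and one tablet is taken each morning.

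On missed doses, Protocol 7.6 says that "subjects should not have missed any double-blind doses of IP within the 2 days before gait testing is performed", and that a subject who has missed one should have the visit moved to another day within the window. Withdrawal is called for when the gap exceeds 3 consecutive days or 5 days in total within a double-blind period. The site must also reconcile returned tablets and account for discrepancies.

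**The concern.** A compliance percentage should treat a missed scheduled dose alike wherever it falls in the period. This one does not. A gap in the middle stays in the denominator because a later dose follows it. A gap at the end drops out because the denominator closes at the last tablet taken.

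The doses that drop out are the ones closest to the gait test, and Protocol 7.6 singles out the last two days before that test. Exactly 3 consecutive missed days does not exceed the withdrawal limit, so such a subject may remain in the trial and contribute a gait measurement while being reported as fully compliant. What is at stake is whether the compliance table can be relied on as background to the gait result.

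**Working it through.** **Inputs.** 50 tablets per bottle and one tablet a day (Protocol 7.1); a nominal 14-day period; visit windows of ±3 days for Visits 4 to 6 (Protocol 8.1), so periods of about 11 to 17 days; the formula and bands from SAP 5.9. Unless stated otherwise, all unused tablets are returned and no other dose is missed.

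**The plan's own figure.** 50 − 14 = 36 tablets over, as Protocol 7.1 states.

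**Formula.** Compliance = 100 × (dispensed − returned) / (last dose date − first dose date + 1).

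**Terminal gap, 14 days, last 3 doses missed.** Taken = 11, returned = 39, last dose on day 11. SAP: (50 − 39)/11 = 11/11 = 100%.

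**Mid-period gap, 14 days, 3 doses missed.** Taken = 11, returned = 39, last dose on day 14. SAP: (50 − 39)/14 = 11/14 = 78.6%.

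**Other cases with doses missed at the end:**

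| Period | Last doses missed | SAP 5.9 | Against scheduled doses |
|---|---|---|---|
| 14 days | 1 | 13/13 = 100% | 13/14 = 92.9% |
| 14 days | 2 | 12/12 = 100% | 12/14 = 85.7% |
| 14 days | 3 | 11/11 = 100% | 11/14 = 78.6% |
| 11 days | 3 | 8/8 = 100% | 8/11 = 72.7% |
| 17 days | 3 | 14/14 = 100% | 14/17 = 82.4% |

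So the percentage is always wrong for a terminal gap, but the band changes only in some cases. Three misses cross 80% in an 11- or 14-day period and do not in a 17-day period; two misses do not cross it in a 14-day period.

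**If the visit is rescheduled.** Suppose the last 3 of 14 doses are missed, the visit moves 2 days later (inside the window), and both extra doses are taken. Taken = 11 + 2 = 13; first to last dose = 16 days; SAP: 13/16 = 81.25%. The gap is now counted, so the formula fails only when testing goes ahead without rescheduling.

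**Unreturned bottle.** If the return is entered as 0, compliance is 50/14 = 357.1%, ranging from 50/17 = 294.1% to 50/11 = 454.5% over the window. Changing the denominator does not cure this, so it needs its own rule.

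**The case against.** The strongest reply is that the protocol already guards against the hidden case. Protocol 7.6 asks for rescheduling, and once dosing resumes the gap is counted. A subject tested regardless has departed from the protocol, and SAP 5.3 tabulates and lists deviations. This stands, and it narrows the point to those subjects. It does not repair the formula: SAP 5.9 still reports them at 100%, and the SAP does not tie the deviation listing to the two-day rule.

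A second reply is that a whole-period percentage cannot show when doses were missed. That is also true. With the corrected denominator, two misses at the end and two in the middle both give 85.7%. The correction makes equal non-compliance score equally; it does not locate it.

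Three stronger readings are tempting, and the documents do not support them:

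- A reader might infer that exposure is overstated for early stoppers. SAP 5.8 tabulates duration separately, from start to stop date and excluding documented interruptions, so someone whose last dose is on day 10 should show 10 days.
- A reader might infer that such a subject's true compliance is 10/14 = 71%. That charges a discontinued subject with doses after stopping. Compliance while on treatment, 10/10 = 100%, is a coherent measure alongside a separate duration, provided it is labelled as such.
- A reader might infer that any lost bottle scores 357%. That needs a 14-day period and a return count entered as 0. If the count is left blank, the no-imputation rule in SAP 4.3 would probably make compliance missing, though SAP 5.9 does not say. If 0 is entered, the value falls above 120% and is visible, though mislabelled as over-use.

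**Conclusion.** The concern holds as a defect of definition in a descriptive table. For a subject who completes a period, SAP 5.9 reports 100% whatever number of doses was missed at the end. In a 14-day period the overstatement is 7.1, 14.3 or 21.4 percentage points for 1, 2 or 3 such misses (100 minus 92.9, 85.7 and 78.6), and the third moves a subject from below 80% into the 80% to 120% band.

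This assumes that earlier doses were taken, unused tablets were returned, the actual last dose date is used, and the gait visit was not rescheduled. How many subjects that describes cannot be judged from the documents.

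It would be wrong to infer that the gait comparison is affected. The percentage does not enter the primary model (SAP 6.3.2) and is not a stated criterion for the ITT, Per-Protocol or Completers populations (SAP 3.1.5 to 3.1.7). The Per-Protocol definition rests on sponsor deviation guidance that is not part of these documents. The absence of a rule for unreturned bottles is a secondary, conditional gap. Overall this is a minor correction worth making.

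**What to change.** Amend SAP 5.9 before database lock:

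- **Subjects who complete a period.** Define expected tablets as the scheduled dosing days from the first dose in the period through the last scheduled dose before the end-of-period visit. For Period II that is the day before Visit 4, because the first tablet from the Visit 4 bottle is taken in clinic. For Period IV it is the corresponding last scheduled dose before the Visit 6 assessments.
- **Subjects who permanently discontinue.** End the count at the discontinuation date and label the result as compliance while on treatment. Do not use the early termination visit date: Protocol 6.6.2 allows that visit to follow the stop, preferably within 7 days, and those days would be counted as missed doses.
- **Unreturned bottle.** State that count-based compliance is set to missing for that period, and that a bottle not returned is not entered as a return of 0.

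The inputs should already exist, since Protocol 7.6 has sites record supplies dispensed, taken and returned at each visit. The cost is a few lines of SAP text and minor programming. The downside is that reported compliance will look slightly less favourable.

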5.10 Overdose

Any occurrence of overdose will be provided in the data listing in the same section of dose administration record.

6 EFFICACY SUMMARIES AND ANALYSES

6.1 General Considerations

Tabulation of the primary and exploratory endpoints will generally be presented for the ITT, Per-Protocol, Completers Population (as described in Section 3), and subgroups (as identified in Section 4.4). The primary efficacy assessments will be performed on the ITT dataset. Sensitivity analysis will be performed on CS dataset. The per-protocol analysis (on the PP population) will also be conducted. If deemed necessary

6.2 Statement of the Null and Alternate Hypothesis

This study will examine the following primary hypothesis:

- H_0 : There is *NO* difference between treatment with intepirdine and treatment with placebo with respect to changes from baseline in gait speed (under single and dual task conditions) at the end of two-week double-blind treatment periods (Period II and Period IV).
- H_a : There *IS* a difference between treatment with intepirdine and treatment with placebo with respect to changes from baseline in gait speed (under single and dual task conditions) at the end of two-week double-blind treatment periods (Period II and Period IV).

The primary comparison of interest will be performed at the 5% level of significance. All hypothesis tests will be two-sided. The primary objective of the study will be considered met only if the primary analyses of both endpoints indicate statistical significance in favor of Intepirdine. No correction for multiplicity will be taken.

6.3 Analyses of the Primary Efficacy Endpoints

6.3.1 Co-Primary Endpoints

The co-primary endpoints in this study are change from baseline in gait speed observed at the end of the two-week double-blind treatment period (Period II and Period IV) under either single or dual task condition.

6.3.2 Primary Efficacy Analyses

Separately by each trial condition, treatment comparisons between intepirdine and placebo in change from baseline in gait speed at the end of the two-week double-blind treatment period (Period II and Period IV) will be analyzed for the ITT Population using a mixed model for crossover design with restricted maximum likelihood estimation and an unstructured covariance matrix. Degrees of freedom will be calculated using Satterthwaite's method.

- This model corrects for dropouts and missing values replacement is not necessary.
- Therefore, no imputation of the missing values will be made or required and the data used in the analysis will be the actual observed responses.
- The statistical model will be fitted initially with sequence, treatment, period, baseline value, both stratification factors (ie, MMSE and dementia type), sex, dementia type by treatment interaction as fixed effects and with subject within sequence as a random effect.
 - If the effects of sex and/or dementia type by treatment interaction are not statistically significant ($p > 0.10$), they will be removed from the final analysis model.
 - If the sequence effect is statistically significant ($p \leq 0.05$) in the model described above, subjects within a sequence will be fitted separately in the model with treatment, baseline value, and both stratification factors (ie, MMSE and dementia type).

The estimated treatment difference for “intepirdine – Placebo” will be displayed together with the 95% confidence interval and the associated p-value.

Least Squares Means will also be presented with the standard error and the number of subjects contributing to the Least Squares Means.

The model will be fitted using SAS PROC MIXED procedure with restricted maximum likelihood estimation and an unstructured covariance matrix. The unstructured covariance is the least restrictive and generally performs well with limited number of repeated measures per subject and puts no parameters on the data with respect to the covariance structure assumptions.

Only in the unlikely circumstance that there are convergence problems with the analysis will other covariance structures be examined to resolve the convergence issue (ie, we would evaluate other additional variance-covariance structures, including compound symmetry (CS), heterogeneous compound symmetry (CSH), and auto-regressive [AR(1)]). In this

eventuality, the Akaike's Information Criterion (AIC) will be used to determine the optimal variance-covariance structure matrix for the primary comparisons.

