#### **10.4.2. Efficacy Analyses**

Efficacy data will be summarized and listed by treatment and assessment time by period and overall. The between treatment differences for the efficacy endpoints of interest will be estimated using a mixed effect model. Baseline and stratification parameters may be included as covariates of interest. The least squares means, treatment difference and 95% CIs, and P-values will be estimated for efficacy endpoints, which may include but are not limited to the following:

- Change in gait speed as measured on an electronic walkway system from the start to the end of each treatment period with RVT-101
- Change in step time variability as measured on an electronic walkway system from the start to the end of each treatment period with RVT-101
- Change in step length variability as measured on an electronic walkway system from the start to the end of each treatment period with RVT-101
- Change in the mini-BESTest total score and change from baseline in measures of dynamic gait and balance assessed with Opal APDM sensors during the mini-BESTest evaluation from the start to the end of each treatment period with RVT-101
- Change in freezing of gait score and freezing ratio using Opal APDM sensors while turning, from the start to the end of each treatment period with RVT-101
- Change in MDS-UPDRS Parts II and III and PIGD sub-scores from the start to the end of each treatment period with RVT-101
- Change from baseline in UPSIT score from the start to the end of each treatment period with RVT-101

The baseline for the efficacy analysis is defined as the start of each individual treatment period. Carry over effect will be tested and evaluated based on the baseline in each treatment period.

The between treatment comparisons may also be performed using an analysis of covariance model based on Period B data.

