1.4 Randomization and Stratification

Each subject will be randomized 1:1 to one of the following sequences:

- Sequence 1: AB = Intepirdine in Period II and Placebo in Period IV
- Sequence 2: BA = Placebo in Period II and Intepirdine in Period IV

Randomization will be stratified according to Mini Mental State Examination (MMSE) score in the groups of 14-19 points and 20-26 points. Randomization will also be stratified according to whether subjects have AD or LBD.

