2.4 Description of Efficacy Endpoints

2.4.1 Gait Speed

Electronic walkway systems, such as the GAITRite and Zeno Walkway system, are computerized assessment tools that utilize an electronic mat consisting of pressure-sensitive pads that can calculate spatiotemporal gait parameters which include gait speed (Buesing et al., 2015) as the primary efficacy endpoint.

Subjects will undergo the gait assessments under single and dual task conditions, each with 3 trials, at all study visits. All assessments will be done on the Zero Walkway system. The PKMAS software will be utilized to capture and process gait data in the study. The average of the 3 measurements will be used in the statistical analysis.

Each co-primary outcome measures (ie, gait speed assessed under single and dual task conditions) in this study will be tested at two-sided 5% level of significance.

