4.2 Standard Reporting Conventions

Tables, listings, and figures will be prepared in accordance with the current International Conference on Harmonization Guidelines. The information and explanatory notes in the “footer” or bottom of each table and listing will include the following information:

- Date of output generation
- SAS® program name, including the path that generates the output
- Any other output specific details that require further elaboration

All hypothesis tests and confidence intervals will be two-sided at an alpha level of 5%.

Version 9.1 or higher of the SAS system will be used to analyze the data, as well as to generate tables, figures, and listings.

In general, tables will be formatted with a column displaying findings for all subjects combined. The summary tables will clearly indicate the number of subjects to which the data apply and unknown or not performed are distinguished from missing data.

The treatment groups will be referred to in the tables, listings, and figures with the following conventions:

- Intepirdine 35 mg
- Placebo

Data analyses will be performed by, or under the direct supervision of, Axovant Sciences.

Efficacy and safety measures over the course of the study will be presented. Continuous data will be summarized by means, SDs, medians, maximum, minimum, and number of subjects. Categorical data will be summarized by counts and percentages.

Data collected in the CRF, as well as laboratory data, will be provided in data listings, sorted (in general) by sequence, subject, period, and date. For date fields, Day on Treatment will be calculated and presented in these listings.

Deviations from the analyses as described in this SAP will be identified in the final Clinical Study Report. When differences exist between the protocol-described analysis and the SAP, the SAP will take precedence.

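### If the sequence effect reaches p ≤ 0.05, SAP 6.3.2 refits each sequence alone: each refit confounds drug with period, and no rule says which result decides the primary objective

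*SAP*

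**What the plan says.** SAP 1.4 sets a two-period, two-sequence crossover randomized 1:1. The first sequence is "Sequence 1: AB = Intepirdine in Period II and Placebo in Period IV"; the second is the reverse.

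SAP 6.3.2 models the single-task and dual-task conditions separately. The initial model has sequence, treatment, period, the period's own baseline, both stratification factors, sex and a dementia-type-by-treatment term. Then comes a conditional step. "If the sequence effect is statistically significant ($p \leq 0.05$) in the model described above", then "subjects within a sequence will be fitted separately in the model with treatment, baseline value, and both stratification factors". Period is not among the terms of that refit. The same section says the treatment difference will be "displayed together with the 95% confidence interval and the associated p-value".

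Under SAP 6.2 the primary objective is "considered met only if the primary analyses of both endpoints indicate statistical significance in favor of Intepirdine".

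Protocol 10.4.2 contains a related sentence: "Carry over effect will be tested and evaluated based on the baseline in each treatment period". It attaches no decision rule to that test. SAP 4.2 gives the SAP precedence where the two documents differ.

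**The concern.** There are two separate faults.

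- **Confounding.** Splitting the data by sequence discards the comparison that separates drug from time. In AB, all drug data come from Period II and all placebo data from Period IV; in BA it is the other way round. A refit within one sequence is a before-and-after comparison, and it equals the drug effect only if the period effect is exactly zero. That cannot be taken for granted when the same walks are repeated throughout: "Subjects will undergo the gait assessments under single and dual task conditions, each with 3 trials, at all study visits".
- **No deciding result.** Once the rule fires, an endpoint has a pooled estimate, an AB estimate and a BA estimate, each with its own interval and p-value. SAP 6.2 and 6.3.2 do not say whether the refits replace or supplement the pooled result, whether both must be significant, or whether they are averaged. The rule is applied per task condition, so it can also fire for one co-primary and not the other.

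At stake is a primary conclusion that would depend on a choice made after unblinding, possibly between two biased estimates that point in opposite directions.

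**Working it through.** The documents give no effect size, SD or period effect, and SAP 1.3 states that power was not formally calculated. There is therefore no planned figure to reproduce. Steps 1 and 2 need no assumptions; steps 3 to 5 do.

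**1. What each refit estimates.** Let τ be the drug effect on the change in gait speed, and δ = (Period II effect) − (Period IV effect).

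- AB, drug minus placebo = Period II − Period IV = τ + δ
- BA, drug minus placebo = Period IV − Period II = τ − δ
- Simple mean of the two = τ

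Within one sequence the columns intercept, treatment and period have rank 2 of 3, and treatment and period correlate at −1 (AB) or +1 (BA). Adding a period term to a refit is thus impossible: the split itself causes the confounding. With both sequences together, the columns intercept, treatment, period and sequence have rank 4 of 4, so treatment is estimable. The period-specific baseline does not help, because a period effect on the change is still aliased with treatment.

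**2. Results against verdicts.** SAP 6.2 needs one verdict for each of two endpoints. If the rule fires on both, there are 2 × 2 = 4 refit p-values plus 2 pooled ones, and no rule for choosing among them.

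**3. Size in standardized units.** Take no drug effect and a period effect of 0.25, 0.5 or 1.0 SD of the within-subject difference, without covariates. The chance that the sequence favoured by the period effect shows a false significant benefit (noncentral t; nominal 2.5%) is:

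| Total N (per sequence) | 0.25 SD | 0.5 SD | 1.0 SD |
|---|---|---|---|
| 30 (15) | 14.5% | 43.8% | 94.9% |
| 40 (20) | 18.5% | 56.4% | 98.9% |

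The pooled model with period keeps a two-sided error of 0.048 to 0.053 for period effects of 0 to 1 SD.

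**4. Size in cm/s.** Assumed: 36 subjects, between-subject SD 18, visit SD 7, correlation 0.25 between the start and end of a period, correlation 0.7 between endpoints, no carryover. Each setting used 40,000 simulated trials (about 2,000 triggered). Sex and the interaction term were left out, and degrees of freedom were fixed approximately.

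- The rule fires in 5.0% of trials per endpoint, in 8.5% on at least one, and in 7.0% on only one.
- Mean standard error: 2.66 for the AB refit, 1.90 for the pooled model.

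No drug effect, triggered trials:

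| δ (cm/s) | Mean AB / BA refit | AB refit falsely favours drug |
|---|---|---|
| 1 | +1.0 / −1.0 | 5% |
| 3 | +3.2 / −3.0 | 18% |
| 5 | +4.9 / −5.0 | 40% |

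Check: a noncentral t with 16 df and noncentrality δ/2.66 (0.38, 1.13, 1.88) gives 5%, 18% and 42%. The pooled model stays near 2.5%. With full within-subject baseline adjustment the AB rates are 5%, 24% and 50%.

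For visit SD 5 to 9 and correlation r of 0.25 to 0.5, the rates span 4–10%, 12–50% and 25–90%. This is an envelope over two estimators:

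- raw change, SE = √(4·SD²(1−r)/18), largest at SD 9, r 0.25: √13.5 = 3.67
- baseline-adjusted, SE = √(2·SD²(1−r²)/18), smallest at SD 5, r 0.5: √2.08 = 1.44

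With baseline adjustment alone the spans are 5–10%, 16–50% and 37–90%.

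False success on both co-primaries, over all trials, is 0.8% for the pooled model. If the AB refit decides when triggered, it is 0.8%, 1.0% and 1.3% for δ = 1, 3 and 5.

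With a true drug effect of 5 cm/s and δ = 0, each refit detects it in about 40% of triggered trials (pooled 72%), and the two refits disagree on significance in 48%. With δ = 1, 3 and 5 they disagree in 53%, 74% and 91%.

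**5. Does the rule protect against carryover?** Suppose carryover adds λ = 5 cm/s to the AB change in Period IV, with τ = 5 and δ = 0.

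- AB = τ + δ − λ = 5 + 0 − 5 = 0 (bias −5)
- BA = τ − δ = 5 (no bias)
- Pooled = (0 + 5)/2 = 2.5 (bias −2.5)

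In a simulation without covariates (18 per sequence, same visit SD and correlation) the rule fires in 22% of such trials. It fires more often, leaves AB worse than the pooled estimate, and does not say to prefer BA.

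**The case against.** - **The refits may only be supplementary.** The preceding bullet in SAP 6.3.2 refers to a final analysis model, and the wording of the conditional step is loose. This stands as a doubt about intent. But the step sits under the primary efficacy analyses and nothing labels it descriptive. One fit per sequence is its natural reading, and either intent leaves the deciding result unstated.
- **The table specifications are in a separate spreadsheet** (SAP 1). They might show which outputs are planned. They would not necessarily supply a decision rule.
- **The period effect may be small.** The endpoint is change from a baseline taken at the start of each period, and subjects have already walked at Visits 1 and 2, so a stable practice gain largely cancels. This is fair. What remains is any difference between the Visit 3-to-4 and Visit 5-to-6 changes. The 3 and 5 cm/s cases are stress cases that the documents do not support; the aliasing does not depend on them.
- **The simulation is not the SAP model.** Sex, the interaction term and Satterthwaite degrees of freedom are left out, so the decimals should not be pressed.
- **The pooled model was favoured by assuming no carryover.** It too is biased under carryover, by half as much as the AB refit in the case shown. The sequence test may be the SAP's intended carryover screen, although it differs from the baseline-based test in the protocol.
- **The practical weight is low.** Overall false success moves from 0.8% to at most 1.3% in a Phase 2 trial. This stands and limits the severity.

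**Conclusion.** The concern holds. Within each sequence treatment and period cannot be separated, and no text in SAP 6.2 or 6.3.2 says which estimate decides after the rule fires; neither point needs an assumed figure. How often and how badly it matters does depend on assumptions. Without carryover the trigger fires in about 5% of trials per endpoint. A period effect of 3 cm/s shifts the two refits about 3 cm/s in opposite directions and raises false benefit in AB to roughly 18% of triggered trials (12–50% over the range examined). The overall false-success rate is barely affected. The harm is an undefined and confounded primary result in the trials where the rule fires, and the rule gives no protection against carryover in return. It should be fixed before unblinding.

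**What to change.** Delete the conditional by-sequence refit from SAP 6.3.2 and replace it with wording such as:

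> *For each co-primary endpoint the primary analysis is the pooled model with sequence, period and treatment, whatever the p-value for sequence. The sequence effect, and gait speed at Visit 3 and Visit 5 by sequence, will be reported as the evaluation of carryover. Any by-sequence results are descriptive.*

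This also supplies the baseline-based carryover evaluation named in Protocol 10.4.2, which the SAP does not set out. If a check robust to carryover is wanted, pre-specify an ANCOVA on Period II data alone, run unconditionally as a sensitivity analysis.

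Separately, the sponsor should clarify the reference in Protocol 10.4.2 to Period B, which is not defined: the periods are numbered I to IV, and B denotes placebo.

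Cost: SAP wording before unblinding and one optional sensitivity table. No new data are needed.
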